12.6 Interim Analysis

No interim analysis is foreseen in this study.

12.7 Measures to Control Bias

12.7.1 Blinding

A certain level of blinding, for study statisticians and study scientists (CRO personnel which will be author of the body SAP), will be required before the body SAP, document describing all the analysis, will be finalized, and signed.

Table 11 Blinding Scheme

| Blinded Study Personnel | End of Blinding Period |
|---------------------------------|---|
| PMP and CRO Study Statisticians | After the SAP finalization. Can be actively unblinded when appropriate. |
| PMP and CRO Clinical Scientist | After the SAP finalization. Can be actively unblinded when appropriate. |

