6.3 Method for Assigning Subjects to Product Sequences

On Day -1, following the re-confirmation of eligibility and completion of baseline procedures, the subjects will be randomized to one of the six sequences of the 3-period cross-over design (Figure 2) by means of a permuted-block schema. Details about the randomization process will be documented in the randomization plan that should contain information about number of blocks, block sizes, block pre-allocation process, stratification, storage of the randomization list and study personal blinding requirements.

The following quotas will be applied on the total number of randomized subjects:

- At least 40% of each sex will be represented

If an adequate number of subjects is already randomized to the study sequences, any additional subjects (except alternate subjects) will be discontinued from the study prior to randomization and will enter the 3-day Safety follow-up period (Section 9.6).

Block size and other randomization details will be available in the randomization plan. The randomization scheme will be generated by an independent statistician and neither the Sponsor staff, nor Investigator or study subjects will have access to the randomization scheme during study conduct.

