6.4 Blinding

This is an open-label study. Therefore, the subjects, the Investigator, the PMP and CRO personnel will be unblinded to the subject's sequence and product use.

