12.2.4 Pharmacokinetics Population

The Pharmacokinetic (PK) Population is a subset of the randomized population and consists of all randomized subjects for whom at least one nicotine PK parameter can be derived. Only subjects without major protocol deviations, as defined in the SAP, which have an impact on evaluability of the main objective, as described in Section 3.1, will be included in the PK population.

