#### **4.4.1 Protocol Deviations**

Protocol deviations are considered as deviations from the study procedures as defined in the study protocol, including but not limited to, as any violation of inclusion/exclusion criteria, mis-randomizations, assessments not performed or performed outside the scheduled time

Philip Morris Products S.A.  
 THS Induction device and regular or menthol sticks, P1-PK-12  
 [REDACTED] CA39924

---

windows, or use of drugs that are known to affect components of the “smokers’ health profile.”

Major protocol deviations are a subset of protocol deviations that may significantly impact the completeness, accuracy, and/or reliability of the study data or that may significantly affect a subject's rights, safety, or well-being.

Subjects with major protocol deviations will be identified to determine whether they will be excluded from any of the analysis populations.

Major deviations will include but are not limited to the deviations presented in Table 4.1.

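### Protocol Sections 6.3, 6.4 and Table 11 do not agree on who is blinded, and Table 11 lets the blind end while exclusions for major deviations are still open

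*Protocol*

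**What the plan says.** **Who is blinded.** Protocol Section 6.4 calls the study open-label and continues: "Therefore, the subjects, the Investigator, the PMP and CRO personnel will be unblinded to the subject's sequence and product use". It names no exception and does not refer to Section 12.7.1. Section 12.7.1, under the heading on measures to control bias, asks for some blinding of statisticians and scientists. Table 11 lists "PMP and CRO Study Statisticians" and the clinical scientists of both organizations as blinded. Section 6.3 adds that "neither the Sponsor staff, nor Investigator or study subjects will have access to the randomization scheme during study conduct".

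**When the blind ends.** Section 12.7.1 says that this blinding "will be required before the body SAP, document describing all the analysis, will be finalized, and signed". For both rows, Table 11 gives the end as "After the SAP finalization. Can be actively unblinded when appropriate".

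**How subjects leave the PK population.** Protocol Section 12.2.4 and SAP Section 4.4 keep subjects with at least one derivable nicotine PK parameter and without major deviations "which have an impact on evaluability of the main objective". SAP Section 4.4.1 adds: "Subjects with major protocol deviations will be identified to determine whether they will be excluded from any of the analysis populations". One major category in SAP Table 4.1 covers a deviation from any study procedure. The protocol gives that same description to a major category (Table 9) and to a minor one (Table 10).

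**The concern.** Two things are unsettled. A reader of Section 6.4 would give statisticians and scientists the product sequence from the start, while a reader of Table 11 would withhold it until the SAP is signed.

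Second, Table 11 ties the end of the blind to a document rather than to the decisions that the document leaves open. Whether a given deviation affects evaluability is judged subject by subject. If the people judging can already see product and nicotine concentration, the choice can be influenced by the result, knowingly or not. With 30 subjects, one or two exclusions are enough to move the main THS/CIG ratios visibly.

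**Working it through.** The plan states no figure on this point, so there is none to reproduce. The first two steps compare text; the third is an illustration of size.

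**1. Do the blinding statements agree?** Table 11 can be read as a time-limited exception to Section 6.4, but neither section says so. Section 6.3 is compatible with Section 6.4 if it means only the randomization list and not the sequence of a subject already randomized, but that is not stated either. The SAP has no blinding section, and its Section 9 declares it aligned with the protocol, so it does not settle the matter.

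**2. Is a judgement still open when the blind may end?**
- Protocol Section 12.1 puts all analyses after SAP finalization, which is the point from which Table 11 permits unblinding.
- SAP Section 4.4.1 speaks of exclusion in the future tense and as a question still to be decided.
- The evaluability test and the catch-all procedural category leave room for judgement.
- Use of another tobacco or nicotine product is a major deviation that could remove the whole subject (Protocol Table 9, SAP Table 4.1). It is also an intercurrent event that sets only the affected period to missing (Protocol Section 12.4.1). The documents do not say which rule prevails.
- Neither document plans a blinded data review or dates the population assignment. That exclusions follow the end of the blind is therefore an inference from the SAP's wording.

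**3. How far could one exclusion move a ratio?**

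Inputs:
- n = 30 (Protocol Section 12.7.3).
- Log-scale SD of Cmax = 0.8. Protocol Section 12.7.3.1 gives a common GSD of 0.8, read here as the SD of log Cmax.
- Within-subject correlation ρ. Section 12.7.3.1 names it but gives no value, so it is varied from 0.5 to 0.9.

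Formulas:
- SD of a subject's log(THS/CIG): D = √(2 × 0.8² × (1 − ρ)).
- Dropping one subject lying 2D below the mean of 30 raises the mean log ratio by 2D/29.
- Dropping two such subjects raises it by 4D/28.

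| ρ | D | one dropped: log shift | ratio | two dropped: log shift | ratio |
|---|---|---|---|---|---|
| 0.5 | √0.640 = 0.800 | 1.600/29 = 0.055 | +5.7% | 3.200/28 = 0.114 | +12.1% |
| 0.8 | √0.256 = 0.506 | 1.012/29 = 0.035 | +3.6% | 2.024/28 = 0.072 | +7.5% |
| 0.9 | √0.128 = 0.358 | 0.716/29 = 0.025 | +2.5% | 1.431/28 = 0.051 | +5.2% |

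A simulation that dropped the single lowest of 30 subjects gave median shifts of 5.6%, 3.5% and 2.5% at the same correlations, which agrees.

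For scale, compare one exclusion with the 95% confidence half-width on the log scale, assuming equal variances and 90 − 30 − 2 − 2 = 56 degrees of freedom (t = 2.003). The half-width is 2.003 × D/√30, so the ratio of shift to half-width is (2/29) × √30/2.003 = 0.19, whatever the correlation.

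If the 0.8 is instead a geometric CV, the log SD is √ln(1 + 0.64) = 0.703. The single-exclusion shift then becomes 2 × 0.703/29 = 0.048 (5.0%) at ρ = 0.5 and 2 × 0.703 × √0.2/29 = 0.022 (2.2%) at ρ = 0.9.

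**The case against.** The other side has several good points.

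- **The study is open-label and descriptive.** Its main endpoints come from an assay, and there is no hypothesis, success criterion or significance level. No decision threshold can be crossed. This stands and limits the severity.
- **A moved ratio would be visible.** SAP Section 6.4 repeats the PK summaries in the randomized population if the two populations differ by one subject. The shell for the ratio table (ITPStat1) adds a column for population, and excluded subjects are listed in Appendix 16.2.3.1. This is real protection, but partial: the randomized population itself drops subjects who violated eligibility criteria or lacked full eligibility documentation (Protocol Section 12.2.3).
- **Much is handled by rule.** Non-adherent periods are set to missing, eligibility violators are removed, and missing or mistimed PK samples are classed as minor. This narrows the discretion without closing it, because the procedural category and the evaluability test remain. Sharper category definitions would help too.
- **Other documents may cover it.** The randomization plan is to hold blinding requirements (Section 6.3), and deviation handling is left to SOPs or the data management plan (Section 11.1.2). We have not seen these. The claim is only that the protocol and SAP do not require the sequence.

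A reader might go further and infer that Section 6.4 and Table 11 cannot both be followed, or that the existing blind is worthless. The documents do not support either. Table 11 can be an exception to Section 6.4, and blinding until SAP signature does protect the choice of model and deviation categories. A reader might also want full PK-population membership fixed before any concentration is seen. That is not possible: membership needs a derivable parameter, and SAP Section 6.3 calculates none for subjects with fewer than three consecutive quantifiable post-use time points.

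**Conclusion.** The point holds as an inexpensive improvement. The three blinding statements need reconciling, and Table 11 allows unblinding while the SAP still leaves deviation-based exclusions to judgement. That the exclusions come later is inferred from the SAP's wording, since neither document dates them.

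The size is modest. One exclusion at 2 SD moves a THS/CIG ratio by about 5.7% to 2.5% for correlations of 0.5 to 0.9, about one-fifth of the confidence half-width. This rests on a log SD of 0.8, an assumed correlation, and an excluded subject who also happens to be extreme. It shows how far such a choice could reach and is not a forecast of bias; nothing in the documents suggests that exclusions will be chosen by result.

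**What to change.** 1. In Protocol Section 6.4, state that the roles in Table 11 are exempt from the unblinding statement for the period given there. In Section 6.3, say what withholding the randomization scheme covers, so that the three sections agree.
2. In Table 11, replace the end of blinding for both rows with: *after written sign-off of protocol-deviation classification and of deviation-based exclusions, completed before product allocation and plasma nicotine results are released to these roles*. Align the text of Section 12.7.1.
3. In SAP Section 4.4, say that the remaining PK-population criterion, at least one derivable parameter, is applied mechanically under SAP Section 6.3 after release.

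The cost is a short amendment and a small delay while results are held until sign-off. No extra data are needed. Two limits remain. Some deviations, such as the wrong product being given, reveal the product by their nature, so withholding concentrations is the more important half. The investigator's case-by-case decision on samples after an eligibility violation (Protocol Section 5.4) also lies outside Table 11 and would not be covered.

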12.7.2 Multiple Testing Procedures

Not applicable.

12.7.3 Determination of Sample Size and Power Consideration

In this study 30 subjects will be randomized to 6 product use sequences, i.e., all full crossover sequences for three investigational products (THS regular, THS menthol and CIG). This sample size is empirically based as there are no considerations for statistical hypothesis.

In an analysis of confidence interval precision on the THS / CIG C_{max} ratios, performed with SAS 9.4 using 10,000 simulations.

The precision of C_{max} ratios has been determined to be of 0.191 or less.

12.7.3.1 Assumptions

The precision has been determined using the following geometric mean (GeoM), geometric coefficient of variation (GCV) and within subject correlation assumptions for C_{max} :

- The GeoM of C_{max} is assumed to be 10, 12, 14 ng/mL for THS menthol, THS regular and CIG respectively with a common GSD of 0.8. These are derived from the following study results.

Confidentiality Statement

Data and information contained in this document are considered to constitute trade secrets and confidential commercial information, and the legal protections provided to such trade secrets and confidential information are hereby claimed under the provisions of applicable law. No part of this document may be publicly disclosed without the written consent of Philip Morris Products S.A.

| Study | ZRHM-PK-06-US | ZRHM-PK-05-JP | ZRHR-PK-01-EU | ZRHR-PK-02-JP | | | | |
|--------------------------------|---------------|---------------|---------------|---------------|-------|-------|-------|-------|
| Product | THS | CIG | THS | CIG | THS | CIG | THS | CIG |
| GeoMean (Stat Desc) | 7.4 | 13.8 | 10.7 | 12.09 | 9.62 | 12.42 | 14.3 | 13.82 |
| GeoCV % (Stat Desc) | 99.83 | 97.35 | 171.0 | 87.71 | 84.26 | 56.13 | 82.82 | 84.00 |

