- d. Intrauterine device, intrauterine system, barrier methods of contraception (condoms, occlusive caps) with spermicidal foam/gel/film/suppository, hormonal contraception, vasectomized partner(s), or true abstinence (periodic abstinence and withdrawal are not effective methods) from Screening until the end of the Safety follow-up period.

Sample Size:

The sample size is empirically based as there are no considerations for statistical hypotheses. A total of 30 subjects is expected to be sufficient to obtain a precision of 0.2 or lower on the THS / CIG C_{max} ratios.

Confidentiality Statement

Data and information contained in this document are considered to constitute trade secrets and confidential commercial information, and the legal protections provided to such trade secrets and confidential information are hereby claimed under the provisions of applicable law. No part of this document may be publicly disclosed without the written consent of Philip Morris Products S.A.

Investigational Product:

Test product: The THS induction device, and regular and menthol sticks, will be provided by the Sponsor. The following two stick variants will be investigated:

| Name in the study | Flavor |
|-------------------|---------|
| P1R stick | Regular |
| P1M stick | Menthol |

Comparator product: The subjects will bring their own supply of commercially available single brand CIG for the study duration.

Duration of Study:

The entire study per subject will last up to 34 days. This will include a screening period of up to 27 days prior to Baseline (Day -28 to Day -2), 4 days of confinement (from the subjects' admission on Day -1 to time of Discharge on Day 3, including 3 overnight stays), and a 3-day Safety follow-up (SFU) period (from time of Discharge on Day 3 or Early termination plus three days). The end of the study (EOS) for a subject is defined as the end of the SFU period. The end of the whole study corresponds to the individual EOS of the last subject.

Statistical Methods:

Demographics and baseline characteristics will be analyzed on the randomized and PK populations.

PK and PD endpoints will be analyzed on the randomized and the PK population.

Safety will be analyzed using the safety population.

Nicotine PK endpoints will be derived from the plasma nicotine concentrations. Nicotine PK parameters will be derived from plasma nicotine concentration versus time data using a non-compartmental analysis (NCA) technique.

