12.7.3.2 Method

The analysis of confidence interval precision on the THS / CIG C_{max} ratios has been implemented using SAS version 9.4, simulating 10000 sets of log-transformed data for 30 subjects with the assumptions described in section 12.7.3.1, and the 6 sequences of this full cross-over design.

The statistical analysis has been performed with a linear model with repeated measurement including as fixed effect the sequence, the period, and the product exposure.

The THS / CIG C_{max} ratios and related confidence intervals have been determined by using the exponential of the difference between THS variants and CIG on the log-transformed data.

Then precision has been determined as the 90th percentile of the 95% confidence interval of the THS / CIG C_{max} ratios.

Confidentiality Statement

Data and information contained in this document are considered to constitute trade secrets and confidential commercial information, and the legal protections provided to such trade secrets and confidential information are hereby claimed under the provisions of applicable law. No part of this document may be publicly disclosed without the written consent of Philip Morris Products S.A.

13 Administrative Considerations

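### Does it matter that the planned precision of 0.191 for n = 30 cannot be reproduced from Protocol 12.7.3?

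*Protocol*

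**What the plan says.** The Synopsis (Sample Size) states that "A total of 30 subjects is expected to be sufficient to obtain a precision of 0.2 or lower" on the THS/CIG Cmax ratios. Protocol 12.7.3 reports that the precision of the Cmax "ratios has been determined to be of 0.191 or less", and both places describe the sample size as empirical, with no hypothesis behind it.

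Section 12.7.3.1 says the calculation rests on geometric means and on "geometric coefficient of variation (GCV) and within subject correlation assumptions" for Cmax. It then has a single bullet: means of 10, 12 and 14 ng/mL for "THS menthol, THS regular and CIG respectively with a common GSD of 0.8". It adds "These are derived from the following study results" and tabulates four earlier studies, whose GeoCVs in per cent are "99.83 | 97.35 | 171.0 | 87.71 | 84.26 | 56.13 | 82.82 | 84.00". The abbreviation list expands GSD as geometric standard deviation.

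Section 12.7.3.2 describes 10,000 simulated data sets of 30 subjects, with the ratio and its interval obtained "by using the exponential of the difference between THS variants and CIG on the log-transformed data". It ends: "Then precision has been determined as the 90th percentile of the 95% confidence interval" of the ratios. The SAP has no sample-size section.

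**The concern.** Three inputs to the only quantitative support for n = 30 are mislabelled or missing.

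- **The scale of 0.8.** A geometric SD is the exponential of the log-scale SD, so it is at least 1. The label cannot be right.
- **The correlation.** In a crossover the within-subject correlation largely decides how wide the interval is. The section announces an assumption and gives no number, and per-product summaries from earlier studies cannot supply one.
- **The quantity called precision.** An interval is two numbers and has no percentile of its own. After exponentiation it is asymmetric, so the half-width, the two arms and the full width all differ.

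If these gaps hid an unfavourable assumption, the claim of 0.2 or lower could fail without anyone being able to tell. Nor could a reader of the study report say whether the planned precision was reached.

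**Working it through.** **Inputs from the documents.** n = 30; six sequences and three periods; two-sided 95% CIs; assumed ratios 12/14 = 0.857 (regular) and 10/14 = 0.714 (menthol); the value 0.8; the eight GeoCVs. **Assumed here, because the documents give no value:** the correlation ρ, the scale of 0.8 and the CI quantity.

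**Step 1: the scale of 0.8.** Converting each GeoCV by log-SD = √ln(1 + CV²):

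| GeoCV % | 99.83 | 97.35 | 171.0 | 87.71 | 84.26 | 56.13 | 82.82 | 84.00 |
|---|---|---|---|---|---|---|---|---|
| log-SD | 0.832 | 0.816 | 1.169 | 0.755 | 0.732 | 0.523 | 0.723 | 0.731 |

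The mean is 0.785 and the root mean square 0.803; the corresponding true GSDs run from 1.69 to 3.22. So 0.8 fits a log-scale SD, equivalent to a GSD of exp(0.8) = 2.23 and a GCV of √(exp(0.64) − 1) = 95%. The match leans on the 171.0% entry: without it the mean is 0.730 and the root mean square 0.736. Since the lead-in announces a GCV, 0.8 could also mean 80%, that is a log-SD of √ln(1.64) = 0.703.

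**Step 2: the formula.** With within-subject SD s_w = s√(1 − ρ), the log difference between two products has SE = s_w√(2/30). The CI half-length on the log scale is h = t × estimated SE. On the ratio scale the half-width is R·sinh(h), the full width twice that, the lower arm R(1 − e^−h) and the upper arm R(e^h − 1), where R is the estimated ratio. Precision is the 90th percentile over 400,000 draws of R and the SE. Degrees of freedom are bracketed by 56 (90 observations − 30 subjects − 2 periods − 2 products) and 28. A REML fit with the planned heterogeneous compound-symmetry structure gave about 47 at ρ = 0.8, inside that bracket.

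One case by hand: s = 0.8 and ρ = 0.8 give s_w = 0.8 × √0.2 = 0.358 and SE = 0.358 × √(2/30) = 0.0924. With t = 2.003, h = 0.185 and the half-width at the assumed ratio is 0.857 × sinh(0.185) = 0.160. The 90th percentile over sampling variation raises this to 0.187 (56 df) or 0.197 (28 df). The REML fit gave 0.189.

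**Step 3: which ρ gives 0.191 for THS regular/CIG (56 df to 28 df)?**

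| Reading of precision | ρ if 0.8 is a log-SD | ρ if 0.8 is a GCV of 80% |
|---|---|---|
| Lower arm | 0.743–0.764 | 0.668–0.695 |
| Half-width | 0.793–0.812 | 0.732–0.757 |
| Upper arm | 0.824–0.841 | 0.773–0.795 |
| Log-scale half-width | 0.829–0.849 | 0.779–0.805 |
| Full width | 0.944–0.950 | 0.927–0.935 |

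On every ratio-scale reading, menthol/CIG is 0.159 when regular/CIG is 0.191, since 0.191 × (10/12) = 0.159. That agrees with the protocol's wording that 0.191 is the larger value.

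**Step 4: how much depends on the missing ρ?** With log-SD 0.8 and 56 df, the half-width for regular/CIG is 0.485, 0.316, 0.235, 0.187 and 0.129 at ρ = 0, 0.5, 0.7, 0.8 and 0.9. Meeting 0.2 as a half-width needs ρ of at least 0.775 (56 df) or 0.795 (28 df).

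**Step 5: does anything use 0.191?** Protocol 12.4.1.4 and SAP 6.5.1 estimate the ratios and their CIs from the trial's own variances; neither the 0.8 nor the assumed correlation enters. Protocol 3.3 sets no success criterion, and 12.1.4 sets no significance level. Neither document plans to compare the observed intervals with 0.191.

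**The case for a change.** The strongest argument for acting is that the protocol chose to publish a figure to three decimals under a heading that promises its assumptions, so those assumptions should be complete. The correlation is no trivial omission: Step 4 shows that it moves the half-width from 0.485 to 0.129. The two readings of 0.8 also give different answers, 0.187 against 0.163 as a half-width at ρ = 0.8. The simulation program must already hold all three items, so supplying them would cost only a few words.

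This stands as a comment on reporting. It does not show that the figure is wrong. It is tempting to add that, at ρ = 0.8, the unnamed quantity alone moves the result from about 0.17 (lower arm) to 0.39 (full width). But that ρ was itself obtained by assuming the half-width. The protocol fixes the result at 0.191, so a different reading changes the implied correlation, not the reported precision. The half-width is the ordinary meaning of CI precision, and under it the protocol's numbers fit together.

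**Conclusion.** The three gaps are real: 0.8 cannot be a GSD, the correlation is not given, and the CI quantity is not named. They make 0.191 impossible to recompute from the text, but they do not make it wrong. Read as a half-width for THS regular/CIG, it is attainable at a correlation of about 0.79 to 0.81 if 0.8 is a log-scale SD (the better-supported reading), or about 0.73 to 0.76 if it is an 80% GCV. Those correlations are back-solved assumptions; the documents neither confirm nor exclude them.

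No change follows, because nothing rests on the figure. The sample size is declared empirical, the study is descriptive, and the reported intervals will take their width from the trial data. Even if the true correlation were lower, the result would be wider intervals, visible as such in the report, with no altered decision rule or analysis. Writing down the missing inputs would leave the sample size, design, analysis and conclusions exactly as they are. The matter is a label slip and omitted detail.
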